### **Interventions**

**Combined home-based exercise group.** Participants in this group will exercise throughout their chemotherapy treatments, starting within 1-2 weeks of its start and ending within 3-4 weeks post-treatment completion .

The exercise intervention will be led by qualified exercise professionals, comprising two weekly 60-minute online exercise group sessions with a 5-minute warm-

up, a 30-minute resistance training, and a 20-minute aerobic exercise component, finishing with a 5-minute cooldown . The warm-up will be composed of mobility and activation movements, such as cat-camels, butterfly chest stretch, overhead reach, floor angels, spine twist in sitting and alternated all fours position, doorway chest stretch, wall slides, scissors, pointer, and single leg stances. The resistance training component will consist of 9 different exercises, performed either with body weight or free weights, completing 2-3 sets of 10-15 repetitions, and will involve movements such as chair sit-to-stand, multi-directional lunges, calf, and toe raises, double-arm and one-arm rows, push-ups, glute bridges, clams, chest press, multi-directional shoulder raises, leg curls, and abdominal exercises (i.e., crunches, leg raises, crisscross) . The aerobic component will consist of low-impact dance exercises, moving large muscle groups to increase heart rate, involving marching, side steps, knee raises, leg curls, multi-directional arm movements, and dance movements . The cooldown will consist of breathing exercises and light stretches. Every exercise professional will follow a written protocol to ensure consistency in the intervention program's application .

Before the beginning of the exercise program, participants will receive an education session on how to use Borg's Perceived Rate of Exertion Scale (RPE) to monitor their effort during aerobic and resistance training and tips on when they may increase the exercise intensity . During the training sessions, participants in the intervention group will be asked to choose their preferred load to execute each exercise in the resistance component, told to perform the aerobic exercises at their preferred speed, and informed that they can stop exercising whenever they need to rest. The exercise professional may suggest increasing loads in specific exercises, but these increases will not be imposed on the participants. Attendance to the sessions in the intervention and control groups will be registered. Additionally, women in this group will be encouraged to perform brisk walking at their preferred intensity and receive a pedometer to increase walking motivation .

**Control group.** Women randomized to the control group will receive weekly 30-minute supervised sessions with breathing, stretching, relaxation exercises, and meditation during the intervention period . Women in this group will not be forbidden to perform PA but will not receive any incentives or advice from the supervising exercise professional.

#### **Criteria for discontinuing or modifying allocated interventions**

Participants will be informed in the pre-study initial meeting that they may leave the study anytime. Participants will be asked to refrain from continuing the intervention if a worsening clinical condition prevents them from exercising and performing the

assessments safely. The exercise program might be reviewed and tailored to the participants' condition across the intervention.

### **Strategies to improve adherence**

Before implementing this study, a survey and focus-group-based study will be performed to adjust the exercise program to the preferences, perceived barriers, and facilitators of women with a breast cancer diagnosis, considering the environmental and cultural context from where the intervention will be conducted. The supervising professional will monitor adherence to the supervised sessions through presence registration. This study will also consider the participants' adherence to the control group. To attempt dropout minimization, we will have an active control group.

### **Concomitant care**

Physiotherapy treatments prescribed by the participant's primary physician and any exercises prescribed to be performed at home prescribed by the physiotherapist will be allowed during the intervention. Participants in the study will be asked not to engage in other exercise and PA programs or activities outside the program. Participants in the control group will not be prohibited from performing physical activities like brisk walking.

### **Outcomes**

Assessments will be performed at four-time points: baseline ( $T_0$ , 1-2 weeks post-chemotherapy start), mid-treatment ( $T_1$ , planned mid-cycle), post-intervention ( $T_2$ , 3-4 weeks post-chemotherapy finishing), and 3 months post-intervention finishing ( $T_3$ , follow-up). The primary outcome of this study will be the chemotherapy completion rates. Secondary outcomes will include functional performance, body composition, PA levels, sedentary behavior (SB) (i.e., behaviors with energy expenditure  $\leq 1.5$  METs while sitting, or lying ), and quality of life. Demographical information (age, education level, marital status, socioeconomic status), PA history, and clinical history data (disease and treatment history, concomitant comorbidities, and other existing health problems besides BC) will also be collected as covariates in the data analysis.

### **Participant timeline**

\*\*\* Table 1\*\*\*

### **Sample size**

Considering this study design, sample size calculations were made for the primary outcome with a factorial variance analysis with repeated measures as reference statistical analysis, giving an initial estimation of 82 participants. Based on previous findings and considering a 20% dropout, the sample size was estimated at 98 participants with a moderate effect size ( $\alpha=0.05$ ; statistical power=0.80) according to Cohen's D calculations, using G\* Power 3.1 .

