Some evidence has shown that exercise may modulate treatment response through its effects on the tumor and may also improve the tolerability of chemotherapy, making it a potential tool to enhance chemotherapy completion rate (i.e., reception of the planned treatment doses) . So far, evidence shows that exercise does not disrupt chemotherapy delivery, but failed to demonstrate that exercise may increase chemotherapy completion rates . For instance, Mijwel et al. (2020) randomized 240 women to either a resistance and high-interval training group, aerobic and high-interval training group, or usual care groups and found no effects of exercise on chemotherapy completion rate. Sanft et al. (2023) conducted a home-based exercise and nutrition counseling intervention on 173 women with BC undergoing chemotherapy, reporting no intervention effects in RDI compared to the usual care group.

Home-based exercise interventions (i.e., programs performed inside or in the immediate surroundings of one's home ) are a convenient and flexible strategy with high adherence and proven to be effective and beneficial to improve functional

performance, raising activity levels, reducing symptoms, and improving overall quality of life in women with a BC diagnosis .

The need for a pleasant and sustainable exercise practice may be a relevant topic when considering the psychological and physiological burden and stress that often accompanies women after a BC diagnosis and during the treatment phase when dealing with therapy side effects . Even though some evidence suggests that allowing self-selection of exercise intensity may not be optimal to maximize health or fitness, increasing enjoyment and adherence to exercise practice and creating sustained lifestyle changes can be more beneficial . Although some exercise methods might be highly efficient in potentiating physiological outcomes in women with BC (e.g., high-intensity interval training), they may fail to meet this population's preferences and hinder the sustainability of active lifestyle behaviors after the studies' interventions .

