### **Primary outcome**

**Chemotherapy completion rates.** Chemotherapy completion rates will be assessed at  $T_0$ ,  $T_1$ , and  $T_2$ . This outcome will be reported as the mean RDI ( $\text{mg} \cdot \text{m}^{-2} / \text{wk}^{-1}$ ), which corresponds to a fraction of the planned chemotherapy dose intensity, by dividing the dose of chemotherapy per square meter (of surface area where the drug is related) in each cycle by the number of weeks in a cycle . Information regarding the planned chemotherapy treatment and the effectively received treatment (i.e., dose, type, and duration) will be acquired from medical records after signing the informed consent . A successful chemotherapy completion rate will be considered if the RDI is  $\geq 85\%$  of the planned treatment, as an RDI below this cut-off is associated with a worse disease prognosis and lower treatment efficacy . Calculations to compare the actual chemotherapy dose intensity received and the initially planned dose intensity will be calculated as total milligrams of chemotherapy divided by the product of the body surface (in square meters) and total weeks of treatment . The RDI results from the actual dose intensity received are divided by the planned dose intensity .

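### The stated 80% power for the primary outcome cannot be verified, and for a moderate arm difference in final RDI 82 analysed women give about 61% before adjustment

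*Protocol*

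**What the plan says.** Protocol, Sample size: "sample size calculations were made for the primary outcome", using a "factorial variance analysis with repeated measures as reference statistical analysis, giving an initial estimation of 82 participants". The effect is described only in words, "with a moderate effect size", with reference to Cohen's d, alpha 0.05 and "statistical power=0.80". Then, "considering a 20% dropout, the sample size was estimated at 98 participants". The Abstract gives a recruitment goal of 122.

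Protocol, Primary outcome: "Chemotherapy completion rates will be assessed at" T0, T1 and T2. That is three occasions, while the Outcomes section lists four for the trial as a whole. RDI is received over planned dose intensity, each computed from the total dose and the total weeks of treatment.

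Protocol, Outcomes and Sequence generation: T0 falls 1-2 weeks after chemotherapy starts, and women are randomised after the baseline assessments.

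Protocol, Statistical methods: repeated-measures factorial ANCOVA is planned for primary and secondary outcomes, with t-tests between groups at each time point.

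Protocol, Background and rationale: the evidence so far "failed to demonstrate that exercise may increase chemotherapy completion rates", and both trials described there report no effect.

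**The concern.** A repeated-measures calculation needs fewer women than a single comparison because it credits averaging over visits. In its between-groups form it also assumes the full arm difference at every visit. Neither feature suits this outcome. Hypothesis 1 asks whether completion is better with the intervention, and completion of the whole course is known once, at the end. At T0 the arms have not yet been randomised.

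If the power is overstated, a null result would be read as evidence against a moderate effect when the trial had a substantial chance of missing one.

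**Working it through.** **Inputs.** From the protocol: two arms 1:1, alpha 0.05, power 0.80, moderate effect, 82 analysed, 20% dropout, 98 or 122 enrolled, RDI at three time points. Assumed, because it is not stated: moderate means d = 0.5, which is f = d/2 = 0.25 for two equal groups. Correlations are assumed where shown.

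**1. Reproducing 82.** For the between-groups test with m measurements and correlation rho, the noncentrality is lambda = N f² m / (1 + (m − 1) rho), with 1 and N − 2 df.

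| m | rho | N | lambda | Power |
|---|---|---|---|---|
| 4 | 0.5 | 80 | 80 × 0.0625 × 4 / 2.5 = 8.00 | 0.798 |
| 4 | 0.5 | 82 | 82 × 0.0625 × 4 / 2.5 = 8.20 | 0.808 |
| 3 | 0.5 | 82 | 82 × 0.0625 × 3 / 2 = 7.69 | 0.782 |
| 3 | 0.5 | 86 | 86 × 0.0625 × 3 / 2 = 8.06 | 0.801 |

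So 82 is the answer for four measurements at rho 0.5, and three measurements would give 86. The match is not unique, because three measurements also give 82 in two ways:
- the between-groups test at rho of about 0.45;
- the group-by-time interaction under G\*Power's SPSS-style effect-size option, with lambda = f² (N − 2)(m − 1) = 0.0625 × 80 × 2 = 10.0 and power 0.808 at N = 82 (0.797 at N = 80).

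**2. Final RDI, one value per woman, unadjusted.** With m = 1, lambda = N × 0.0625.

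| Analysed | How reached | lambda | Power |
|---|---|---|---|
| 78 | 98 × 0.8 = 78.4 | 4.875 | 59% |
| 82 | protocol's initial estimate | 5.125 | 61% |
| 98 | 122 × 0.8 = 97.6, or 98 without loss | 6.125 | 69% |
| 122 | 122 without loss | 7.625 | 78% |
| 128 | needed for 80% | 8.000 | 80% |

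**3. Final RDI, adjusted for a baseline covariate with correlation r.** lambda = N × 0.0625 / (1 − r²).

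| r (assumed) | 78 analysed | 82 analysed | 98 analysed |
|---|---|---|---|
| 0 | 59% | 61% | 69% |
| 0.3 | 63% | 65% | 73% |
| 0.5 | 71% | 73% | 81% |
| 0.6 | 78% | 80% | 87% |

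**4. What a zero difference at T0 does to the between-groups test.** Take arm differences of 0, 0.5 and 0.5 SD at T0, T1 and T2, with rho 0.5 (an assumed pattern). The average difference is (0 + 0.5 + 0.5)/3 = 0.333 SD, so f = 0.1667. With 82 women, lambda = 82 × 0.0278 × 3 / 2 = 3.42 and power is about 45%. With 122 it is about 61%.

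**The case against.** **The number of measurements.** A reader might infer that four measurements were entered by mistake for an outcome measured three times. The documents do not support that as a finding: the sample size section gives no number of measurements, and step 1 shows that some three-measurement settings also return 82. Even if the slip occurred, it moves N from 82 to 86 and power from 0.808 to 0.782, which alone is not a serious loss. The error is possible, not proven.

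**The planned analysis.** The primary analysis is a repeated-measures ANCOVA, not a final-value comparison, and Hypothesis 1 does not use the word final. With 98 completers, three measurements and rho 0.5, the between-groups test has 85% power. This is fair, and it makes the 61% conditional. But the 85% assumes 0.5 SD at every visit including T0, which randomisation after baseline rules out in expectation. The interaction route does not rescue the claim either: its f measures the interaction with the within-woman correlation already absorbed, so it implies a 0.5 SD difference in final RDI only under a further unstated correlation.

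**Adjustment.** The 128 and the 61% ignore covariates. This also stands: 61% is the no-adjustment end of a range. The documents give no correlation, and at T0 little of the course has been delivered, so RDI at T0 may predict final RDI poorly. Other covariates could help by an unknown amount.

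**The size of the risk.** A reader might infer that the trial has about a 40% chance of missing a moderate effect whatever happens. That holds, unadjusted, only for 78 to 82 analysed. With 122 enrolled it is 31% after 20% loss (98 analysed) or 22% with none.

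**Prior evidence.** The sample size text appeals to earlier findings beside the dropout figure and may mean the dropout, and the two null trials are introduced as examples. So the protocol is not shown to contradict itself here. It simply describes no finding that supports a moderate effect on RDI.

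**Conclusion.** The concern holds in a limited form. The 80% is stated without the inputs needed to check it. For a 0.5 SD difference in final RDI, 82 analysed women reach about 80% only if a baseline covariate correlates about 0.6 with the outcome. Unadjusted power is 61% with 82, 59% with 78 and 69% with 98. At a correlation of 0.5, 98 analysed would reach 81%, so the shortfall depends on which enrolment figure stands and on a correlation that the protocol does not give.

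The conclusion rests on three assumptions: moderate means d = 0.5, the test is two-sided at 5%, and Hypothesis 1 is answered by RDI over the whole course. The third follows from the definition under Primary outcome but is not stated in the hypothesis.

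**What to change.** - **Sample size.** Name the test and the effect tested, the number of RDI measurements, the correlation and the numeric effect size. Reconcile 98 with 122. Then replace the unqualified 80% by the power for final RDI by arm at the number expected to be analysed after loss: about 59% for 98 enrolled or 69% for 122 enrolled, unadjusted, with the range under stated correlations (for 0.3 to 0.5: 63% to 71%, or 73% to 81%).
- **Effect size.** Describe the moderate effect as an assumption, and state what the appeal to previous findings refers to.
- **Statistical methods.** Name the primary comparison of RDI so that it is the one the calculation describes; otherwise sample size and analysis will disagree.

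The cost is protocol wording and a less favourable stated power. No extra patients are needed. RDI comes from medical records, so final values could be sought for all women. If none were lost, unadjusted power would be 69% with 98 or 78% with 122, but those figures should not be quoted while the Blinding and retention sections exclude data from women who leave or miss assessments.

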## ABSTRACT

**Background.** Chemotherapy drugs carry many side effects that may hinder the functional performance of women with breast cancer (BC). Chemoresistance can lead to treatment failure. A relative dose intensity of chemotherapy <85% is associated with a worse diagnosis and lower treatment efficacy. Exercise may modulate treatment response through its effects on the tumor microenvironment and treatment tolerability. The need for a pleasant and sustainable exercise practice is important, considering the psychological and physiological stress that accompanies women with a BC diagnosis during treatment. Studies investigating the effects of exercise interventions on chemotherapy completion rates are needed.

**Purpose.** This study aims to investigate the effects of a self-selected intensity structured supervised home-based combined exercise intervention on the chemotherapy completion rates of women with BC. Secondly, we intend to analyze the impact of this intervention on functional performance, quality of life, body composition, and physical activity levels. A 3-month follow-up will investigate if physically active behavior is sustained post-intervention.

**Methods.** A 2-arm randomized controlled trial will be implemented in a real-world exercise setting to compare an online structured and supervised group aerobic and strength exercise intervention with an active control group during chemotherapy treatments. The study recruitment goal is 122 women with a BC diagnosis stage I-III who are scheduled to have neoadjuvant or adjuvant chemotherapy. Outcome measures will be obtained at baseline, mid-treatment ( $\approx$ 3 months), post-intervention ( $\approx$ 6 months), and 3-month follow-up. A mediation analysis will also be conducted.

**Key-words:** Breast cancer; Home-based exercise; Chemotherapy; Functional performance; Body composition; Physical activity; Quality of life

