## **Trial design**

This study will be a 2-arm pragmatic and superiority randomized controlled trial with an intervention and an active control group, with a 1:1 allocation ratio. It will comprise a structured, supervised, home-based combined exercise intervention that will start 1-2 weeks after chemotherapy treatments begin and continue until 3-4 weeks post-treatment. Additionally, a 3-month follow-up will be performed. This protocol followed the Spirit guidelines.

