## **Methods**

### **Study setting**

The Home-Combo study will take place in the Algarve, and the sample will be recruited by medical referral from various public and private hospitals, and oncologic organizations across the region.

The intervention design will consider the PA/exercise preferences, perceived barriers, and facilitators of women with BC. This information will be collected before the intervention through a mixed-methods qualitative study that will include a survey and focus groups. The intervention will be conducted online to ensure the participants' safety during the chemotherapy treatment phase, as they may have compromised immunity. Also, this option was made to attenuate participants' burden caused by commuting requirements . Due to the specific timings between the first contact and study enrolment, participants will be enrolled continuously for one year. Recruitment will continue for each cohort until the number of participants per group is achieved. A scheme of the study timeline is presented in Table 1.

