### **Assignment of interventions**

#### **Allocation**

##### **Sequence generation**

After signing the informed consent form, participants will be given a number, randomly generated through Excel and emailed by a non-interventionist team member, which will be their participant number throughout the study. Participants will be instructed not to reveal their number to the research team or the other participants and to keep it with them until the end of the study. After all baseline assessments, participants will be randomly assigned to either the intervention or control arm through an online program (<https://www.graphpad.com/quickcalcs/randomize1/>). If recruitment takes longer than expected, adjustments in allocation may be made.

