### **Blinding (masking)**

Participants will be told they are part of an exercise intervention without any mention of a control group. The healthcare professionals responsible for the chemotherapy prescription and administration and registering all clinical information will be blinded to the participants' groups. None of the research team members will know the number of participants, so data analysis will be performed in a blinded setting. The exercise professional conducting the assessments will be blinded to the participant's number but not to which group the participant belongs. If, at any given moment, a participant reveals her number to a research team member, all posterior data from that participant will be disregarded. If a participant decides to leave the study or must abandon it due to health complications, the team member with the number information will be informed, and all further data will be disregarded from the analysis.

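### The protocol gives two unreconciled sample sizes, 122 and 98, and the 98 under-allows for the stated 20% dropout

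*Protocol*

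**What the plan says.** Two sections of the protocol give a number of women.

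- **Abstract, Methods paragraph:** "The study recruitment goal is 122 women with a BC diagnosis stage I-III".
- **Sample size:** a calculation for the primary outcome, based on a repeated-measures factorial analysis of variance with alpha 0.05 and power 0.80, "giving an initial estimation of 82 participants". The next sentence moves to the final figure: "considering a 20% dropout, the sample size was estimated at 98 participants with a moderate effect size".

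Two other sections bear on how the number is used. Trial design describes two arms "with a 1:1 allocation ratio". Study setting says "participants will be enrolled continuously for one year", and then "Recruitment will continue for each cohort until the number of participants per group is achieved". It does not say what that number is.

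**The concern.** A randomised trial needs one planned size. Here the Abstract and the Sample size section name different totals, and no section explains how one leads to the other. A trial that closed at 98 and a trial that closed at 122 could each claim to have followed the protocol.

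The step from 82 to 98 also looks like the common slip of adding 20% to the required number instead of dividing by the fraction expected to remain. If so, 98 does not protect the 82 from a 20% loss. The 122, for its part, has no stated derivation.

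**Working it through.** **Inputs from the protocol.** Initial estimate 82, dropout 20%, adjusted size 98, alpha 0.05 and power 0.80 (Sample size); recruitment goal 122 (Abstract); allocation 1:1 (Trial design).

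**1. Reproduce the 98.**
- Adding 20%: 82 × (1 + 0.20) = 98.4, stated as 98. This matches.
- Dividing by the fraction retained: 82/(1 − 0.20) = 102.5, so 103, or 104 with equal arms (52 each). This does not match.

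**2. What each total leaves after 20% loss.**

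| Enrolled | Per arm | Left after 20% loss | Largest loss that keeps 82 |
|---|---|---|---|
| 98 | 49 | 98 × 0.8 = 78.4 | 1 − 82/98 = 16.3% |
| 104 | 52 | 104 × 0.8 = 83.2 | 1 − 82/104 = 21.2% |
| 122 | 61 | 122 × 0.8 = 97.6 | 1 − 82/122 = 32.8% |

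The two stated totals differ by 122 − 98 = 24 women, or 12 per arm.

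**3. Where 122 could come from.** Neither rule applied to 82 gives it (98.4 or 102.5). Reaching 122 from 82 by division implies about 33% loss. Numerically, 98/0.8 = 122.5, which would be a second 20% allowance on a figure that already contains one. The protocol does not say this was done.

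**4. Power cost of the inflation step alone.** The protocol gives no numerical effect size, number of measures or correlation, and does not say which effect was powered. The following are therefore assumptions, chosen because they return 82: between-group effect in a repeated-measures analysis, f = 0.25, m = 4 measures, correlation ρ = 0.5.

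- Noncentrality: λ = f² × N × m / [1 + (m − 1)ρ], with 1 and N − 2 degrees of freedom.
- N = 82: λ = 0.0625 × 82 × 4 / 2.5 = 8.2, power 0.808.
- N = 78: λ = 0.0625 × 78 × 4 / 2.5 = 7.8, power 0.787.

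The result for 82 depends on these choices. With four measures, ρ = 0.3 returns 62 and ρ = 0.7 returns 100; with three measures and ρ = 0.5 it is 86. The cost of losing four women is stable all the same: with three measures and ρ = 0.5, power is 0.782 at 82 and 0.761 at 78, again a drop of about 0.02.

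**The case against.** **The two numbers may count different things.** The Abstract speaks of a recruitment goal and the Sample size section of a sample size. Women consent before randomisation ("After all baseline assessments, participants will be randomly assigned to either the intervention or control arm"), so a recruitment goal could properly exceed the number randomised. That is possible, but the protocol never says so and gives no allowance for losses between consent and randomisation. What stands is that the two totals are better called unreconciled than flatly contradictory.

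**98 may be an uninflated requirement.** With f = 0.25, two measures and ρ = 0.5, the same between-group formula returns exactly 98, and 98/0.8 = 122.5 would then be a single correct inflation. This conflicts with the Sample size section, which gives 82 as the initial figure and reaches 98 only after taking dropout into account.

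**The inflation error may not matter.** This stands in large part. It has no consequence if 122 governs, and costs about 0.02 of power if 98 does. That section also does not say in so many words that 82 must remain after dropout; this is the natural reading of an initial estimate followed by a dropout allowance.

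**Study setting may not be affected.** Its phrase about the number per group follows a reference to each cohort, so it may mean the size of a cohort's groups rather than the trial total. It cannot be used to show that the trial's stopping point is ambiguous, only that the phrase needs a number.

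**Conclusion.** The point holds. The protocol carries two current totals, 122 and 98 (61 or 49 per arm), with no link between them. This is the main defect and it rests on the text alone. The 98 is also too small for its stated purpose if 82 is the number needed after 20% loss: about 78 would remain, and 82 is kept only up to 16.3% loss. This part needs only the protocol's own figures. It is minor, at about 0.79 against 0.81 in power, and that power comparison rests on the assumed inputs.

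Three stronger readings are tempting and are not supported:

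- **That the trial is seriously underpowered because of this error.** The shortfall is four women at most, and none if 122 is the target.
- **That 122 shows dropout was applied twice.** The arithmetic fits, but it is an inference.
- **That 78 would be the number analysed.** It is the number remaining. For women who leave, the Blinding section says "all further data will be disregarded from the analysis", while Statistical methods plans an intention-to-treat analysis with missing values filled in. How those rules fit together is a separate question, and this point does not depend on it.

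**What to change.** State one total and its per-arm number, the same in the Abstract and in Sample size, and say in Study setting whether the number per group refers to it.

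- If 82 is the number needed after 20% loss, give 104 in total, 52 per arm.
- If 98 is kept, state that about 78 remain after 20% loss and restate the power from the G\*Power inputs actually used.
- If 122 is the target, state how it was derived.

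In each case, report those inputs: the numerical effect size, the effect tested, the number of measures and the correlation.

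The cost is a change of text and figures, submitted to the ethics committees as the Protocol amendments section requires. No option needs more women than the 122 already stated, and none changes the analysis. If 98 is kept, the stated power may have to be lowered slightly.
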